## 12.3 Statistical Analysis

Data analysis will be carried out with Python  $\geq 3.6$  with statistical package pingouin  $\geq 0.3.10$ . Pingouin will be used to calculate ANOVA results (calculations provided in <https://pingouin-stats.org/generated/pingouin.anova.html#pingouin.anova>). All other calculations will be done according to formulas provided in this section.

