## 7.2 Subject Procedure

### Part 1

The purpose of the procedure in the Part 1 is to calculate the accuracy of Ligence Heart manual functions that are used to perform echocardiographic measurements comparing it with the accuracy of manual measurements performed with other CE marked state-of-the-art medical image viewers. Measurements made in Ligence Heart software will be compared with CE marked software “IntelliSpace Cardiovascular 5.1” (Phillips) and “EchoPAC” version 112 from GE Healthcare.

One cardiologist will perform 2D TTE measurements of each patient on each system 2 times. Time difference between repeated measures must be at least two days.

### Part 2

The purpose of the procedure in the Part 2 is to compare Ligence Heart automatic measurements accuracy and reliability with human cardiologists in real clinical setting.

Four physicians will make 2D TTE measurements of each subject study 2 times. Physicians cannot share thoughts or results between themselves. Time difference between repeated measures must be at least two days. Measurements of three physicians will be used in modeling and results of the 4th will be used as a validation with automated system.

During both parts, time used for the analysis of the 2D TTE images will be recorded. During manual 2D TTE image analysis, time it takes for physician to make measurements will be registered. Stopwatch starts when physician opens study in Ligence Heart and stops when all listed measurements are made. In the use case including automatic measurements, the time it takes for automatic system to make measurements and physician to correct/validate the results is registered.

Summary of the clinical investigation parts

#	Analysis	Purpose	TTE Examination Protocol	Measurements
Part 1	Manual Measurement Analysis	To calculate the accuracy of Ligence Heart manual functions that are used to perform echocardiographic measurements comparing it with the accuracy of manual measurements performed with other CE marked state-of-the-art medical image viewers.	One physician will make 2D TTE measurements of each patient on each system 2 times. Time difference between repeated measures must be at least two days.	
 
• AoS (PLA)
 
• RVB (A4CH)
 
• LVEDV (A4CH)
 
• LVEDV (A2CH)
 
• RVEDA (A4CH)
 
• RAA (A4CH)
 
• AV-Vmax
 

UAB Ligence	Clinical Investigation Report	2021-04-09
		Rev: 1.0

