## 12.4 Manual Functionalities Analysis (Part 1)

### 12.4.1 Statistical Methods Values and Characteristics

Two-way ANOVA – test used to detect any overall differences between related means.

ANOVA characteristics

Source of variation	Degrees of Freedom	Mean Square
Patient	n - 1	MSS
Software	t - 1	MSR

UAB Ligence	Clinical Investigation Report	2021-04-09
		Rev: 1.0

Error (Patient x Software)	(n - 1)(t - 1)	MSSR
Error (Software)	nt(m - 1)	MSE

ANOVA variance components

Estimates of Variance Components
$\hat{\sigma}_S^2 = \frac{MSS - MSE}{mt}$
$\hat{\sigma}_R^2 = \frac{MSR - MSSR}{mn}$
$\hat{\sigma}_{SR}^2 = \frac{MSSR - MSE}{m}$
$\hat{\sigma}_e^2 = MSE$

Intrater reliability coefficient characterizes reliability of two different raters to measure subjects similarly. Coefficient calculation formulas are given below:

$$\rho = \frac{\hat{\sigma}_S^2}{\hat{\sigma}_S^2 + \hat{\sigma}_R^2 + \hat{\sigma}_{SR}^2 + \hat{\sigma}_e^2}$$

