#### 12.4.2 Data analysis

Two-way ANOVA will be employed to test for significant differences between measurements made in different medical imaging software. Interrater reliability coefficient and Pearson correlation coefficient will be calculated to check the level of interchangeability between software.

Intrater reliability coefficient interpretation

Interpretation	Value
Slight	0.00-0.20
Fair	0.21-0.40
Moderate	0.41-0.60
Substantial	0.61-0.80
Almost perfect	0.81-1.00

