## 15.1 Manual functionalities (Part 1)

All measurements performed manually using Ligence Heart were equally accurate and reliable when compared to state-of-the-art certified medical image analysis software. Median inter-software reliability was 95.52% (IQR 94.31 - 97.17) with the lowest value observed for RAA (89.30%) and the highest for APV (99.26%). All tested measurements had inter-software reliability above 0.8, corresponding to high level of agreement between different platforms (**Table 2**) and there was no significant difference in the measurements produced by Ligence Heart in comparison to other CE marked state of the art medical device software.

**Table 2.** Inter-software reliability for Ligence Heart compared to EchoPAC and Intellispace Cardiovascular.

Measurement (abb.)	Measurement (full)	Inter-software reliability
AoS	Aortic sinus diameter	97.81%
RVB	Right ventricle basal diameter	93.28%
LVEDV4A	Left ventricle end diastolic volume (A4Ch)	97.12%
LVEDV2A	Left ventricle end diastolic volume (A2Ch)	93.95%
RVEDA	Right ventricle end diastolic area	92.17%
RAA	Right atrium area	89.30%
APV	Aortic peak velocity	99.26%
PTRV	Peak tricuspid regurgitation velocity	97.18%
E	Transmitral E velocity	99.21%
SP	S prime right ventricle lateral wall	97.16%
Dec	Transmitral E velocity deceleration time	95.41%
ACT	Acceleration time	95.52%
AVVTI	Aortic valve maximum velocity time integral	98.21%
TR VTI	Tricuspid regurgitation velocity time integral	94.66%
LVEDV	Left ventricle end diastolic volume (biplane)	95.52%

UAB Ligence	Clinical Investigation Report	2021-04-09
		Rev: 1.0

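### The ANOVA function named for the Part 1 software comparison divides by repeat-reading error instead of patient-by-software error, so its p-values are too small whenever software differences vary between patients

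*Protocol*

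**What the plan says.** Section 12.3 states "Pingouin will be used to calculate ANOVA results" and identifies the routine by its documentation page: "calculations provided in <https://pingouin-stats.org/generated/pingouin.anova.html#pingouin.anova>". It then says "All other calculations will be done according to formulas provided in this section". No formula in section 12 gives an F ratio, so F and p can only come from the output of the named function.

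Section 12.4.1 describes the two-way ANOVA as a "test used to detect any overall differences between related means". Its table has two error lines. One ("Error (Patient x Software") has mean square MSSR on (n-1)(t-1) degrees of freedom; the other, for repeat readings, has MSE on nt(m-1). The table does not say which is the denominator for software. Section 12.4.2 then gives the test its role: "Two-way ANOVA will be employed to test for significant differences between measurements made in different medical imaging software".

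Section 7.2 sets the design: "One cardiologist will perform 2D TTE measurements of each patient on each system 2 times". The systems are Ligence Heart and two comparators. Section 15.1 on manual functionalities reports that "there was no significant difference in the measurements produced by Ligence Heart in comparison to other CE marked state of the art medical device software".

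**The concern.** When every patient is read on every system, software means must be judged against how much software differences vary from patient to patient. Scatter between one reader's two repeats measures something else and is normally smaller. A function that accepts only between-subject factors does not make this distinction and uses the repeat scatter for both main effects. The named calculation is then not the related-means test that section 12.4.1 describes.

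This is the only significance test planned for hypothesis 1, and it is applied to 15 measurements. Where the interaction is not negligible, it will declare software differences that do not exist at well above 5%, and the sponsor's own device would bear the false alarms. Anyone reusing section 12 for the wider validation announced in section 16.4 would inherit the problem.

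**Working it through.** **Inputs.** t = 3 systems and m = 2 readings (section 7.2); planned n = 54 (section 12.2); enrolled n = 58 (section 15.1, demographic data); alpha = 0.05 (section 12.2). The document reports no mean squares, so the ratio r of patient-by-software variance to repeat-reading variance is an assumption, run from 0 to 2.

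**The plan's own figure.** For the within-between interaction in section 12.2, the noncentrality is f²·N·m/(1-ρ) = 0.0625 × 54 × 2/0.4 = 16.875 on 2 and 51 df. Power is 0.9555 at N = 54 and 0.9518 at N = 53. The smallest N is 53, or 54 in three equal groups, so the stated 54 reproduces. It was sized for a different effect from the software main effect and does not bear on this point.

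**Which denominator is right.** Section 12.4.1 estimates the software component as (MSR - MSSR)/(mn) and the interaction component as (MSSR - MSE)/m. Read as expectations:
- E[MSE] = σe²
- E[MSSR] = σe² + mσSR²
- E[MSR] = σe² + mσSR² + mnσR²

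With σR² = 0, MSR and MSSR share an expectation. MSR exceeds MSE by the factor 1 + m·r = 1 + 2r.

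**What the named function does.** In pingouin 0.6.1, which meets the protocol's minimum of 0.3.10, the balanced two-way code divides both main effects by the residual mean square. Two simulated 58 × 3 × 2 data sets with no software effect and r = 1 show the consequence.

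| Data set | MS software | MS interaction | MS residual | MSR/MSE on (2, 174) df | MSR/MSSR on (2, 114) df |
|---|---|---|---|---|---|
| A | 3.461 | 3.005 | 0.998 | F = 3.47, p = 0.033 | F = 1.15, p = 0.32 |
| B | 0.853 | 2.546 | 0.859 | F = 0.993, p = 0.372 | F = 0.335, p = 0.716 |

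In data set A the choice of denominator decides significance. In B the result on the interaction denominator is the same as from pingouin's repeated-measures function.

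**Exact type I error of MSR/MSE.** Under the null, MSR/MSE is distributed as (1 + 2r) times a central F. The rate is therefore P(F[2, 174] > 3.048/(1 + 2r)), where 3.048 is the 5% critical value at n = 58.

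| r | 1 + 2r | 3.048/(1 + 2r) | Type I error |
|---|---|---|---|
| 0 | 1.0 | 3.048 | 5.0% |
| 0.1 | 1.2 | 2.540 | 8.2% |
| 0.25 | 1.5 | 2.032 | 13.4% |
| 0.5 | 2.0 | 1.524 | 22.1% |
| 1 | 3.0 | 1.016 | 36.4% |
| 2 | 5.0 | 0.610 | 54.5% |

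At the planned n = 54 (162 error df) the figures are practically the same. Simulated type I error of MSR/MSSR, with 20,000 runs per setting, was 4.8% to 5.3% at every ratio tried.

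**Effect on a non-significant result.** If MSSR ≥ MSE in the data, MSR/MSSR cannot exceed MSR/MSE, and its critical value is higher (3.076 on 2 and 114 df). A measurement that was non-significant on MSE then stays non-significant. Allowing for sampling, with software noncentrality 0, 2 and 5, the chance of a switch to significance is at most 0.08% at r = 0.25, about 0.002% or less at 0.5, and zero in 200,000 draws at 1 and 2. It exceeds 1% only at r of 0 to 0.1, where the named test is valid or nearly so.

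**The case against.** The strongest reply is that the protocol never writes an F ratio. It gives a software link and a table of mean squares, its variance components already set MSR against MSSR, and a SAP could settle the denominator. This stands in part: the denominator is inferred from the function, not quoted from the text. But section 12.3 does more than leave a gap. It assigns the ANOVA results to one routine, and that routine's denominator can be checked and is wrong for this design.

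One could also treat the patients as fixed, which would make MSE legitimate. That does not fit the plan: section 6.6 draws studies at random from 17,410, section 12.4.1 gives patients a variance component, and hypothesis 1 is a general claim about the software.

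The reply is right about reach. A reader might infer that the Part 1 conclusion in sections 15.1 and 16.1 falls with the test. The documents do not support that: the error makes p too small, so a non-significant result obtained this way survived a test biased towards finding differences. A reader might also infer that the inter-software reliability is compromised. It is not, because it uses the mean squares, which the function computes correctly. Reliability is endpoint 1 in section 5.3.1 and the whole content of Table 2. Nor are confidence intervals distorted, since Part 1 plans neither an interval for a software difference nor an equivalence analysis. Reading non-significance as equal accuracy is a separate weakness, which this correction neither causes nor cures.

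**Conclusion.** The point holds as a fault in the stated calculation. For a crossed design the named function gives software p-values that are too small whenever patient-by-software variance is above zero. The inflation depends on a ratio the document does not report, so the upper rates (36.4% at r = 1, 54.5% at r = 2) must not be read as the error actually incurred in this study. The figures assume normal errors, balanced data and patients as a random sample.

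The consequence is limited. Only F and p for software in Part 1 are affected. The Part 2 SEM and MDC also rest on the unaffected mean squares. Provided the reported non-significance came from the planned test, it would almost surely stand after correction. The plan should be corrected because it prescribes an invalid test, not because the reported finding is shown to be wrong.

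**What to change.** In sections 12.3 and 12.4.2, state that software is tested with F = MSR/MSSR on (t-1) and (n-1)(t-1) degrees of freedom. Either a repeated-measures ANOVA on the patient-by-software means of the two runs, or a mixed model with random patient and patient-by-software terms, would do this. Keep the two-way table as the source of the mean squares for the reliability coefficient. Recompute the 15 Part 1 p-values from the stored readings and report them.

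The cost is one sentence in the statistics section and a rerun of 15 analyses, with no new data. Error degrees of freedom at n = 58 fall from 58 × 3 × 1 = 174 to 57 × 2 = 114, which moves the 5% critical value only from 3.048 to 3.076.

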## 12.4 Manual Functionalities Analysis (Part 1)

### 12.4.1 Statistical Methods Values and Characteristics

Two-way ANOVA – test used to detect any overall differences between related means.

ANOVA characteristics

Source of variation	Degrees of Freedom	Mean Square
Patient	n - 1	MSS
Software	t - 1	MSR

UAB Ligence	Clinical Investigation Report	2021-04-09
		Rev: 1.0

Error (Patient x Software)	(n - 1)(t - 1)	MSSR
Error (Software)	nt(m - 1)	MSE

ANOVA variance components

Estimates of Variance Components
$\hat{\sigma}_S^2 = \frac{MSS - MSE}{mt}$
$\hat{\sigma}_R^2 = \frac{MSR - MSSR}{mn}$
$\hat{\sigma}_{SR}^2 = \frac{MSSR - MSE}{m}$
$\hat{\sigma}_e^2 = MSE$

Intrater reliability coefficient characterizes reliability of two different raters to measure subjects similarly. Coefficient calculation formulas are given below:

$$\rho = \frac{\hat{\sigma}_S^2}{\hat{\sigma}_S^2 + \hat{\sigma}_R^2 + \hat{\sigma}_{SR}^2 + \hat{\sigma}_e^2}$$

#### 12.4.2 Data analysis

Two-way ANOVA will be employed to test for significant differences between measurements made in different medical imaging software. Interrater reliability coefficient and Pearson correlation coefficient will be calculated to check the level of interchangeability between software.

Intrater reliability coefficient interpretation

Interpretation	Value
Slight	0.00-0.20
Fair	0.21-0.40
Moderate	0.41-0.60
Substantial	0.61-0.80
Almost perfect	0.81-1.00

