## 5.3 Study Endpoints

### 5.3.1 Primary Endpoints

The end points respectively to the objective number:

4. Echocardiographic measurements performed manually with Ligence Heart and comparator software. The inter-software reliability between manual measurements performed with Ligence Heart and other CE marked state-of-the-art medical image viewers will be calculated (Part 1 of the investigation);
5. Echocardiographic measurements performed automatically by Ligence Heart software and echocardiographic measurements performed manually by physicians. The accuracy of automatic functions of Ligence Heart will be compared with the accuracy of physicians performing measurements manually (Part 2 of the investigation);
6. Time used to perform echocardiographic measurements manually and time used to perform the measurements automatically.

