# 7 Study Procedures

## 7.1 Study Parts

No direct clinical procedures will be performed on the enrolled subjects. The procedure that will take place is the analysis of the 2D TTE examination DICOM images that were included in this study. Once enough subjects are chosen and enrolled in the study, the following parts take place:

During Part 1 of the study, investigators will analyze the same images using Ligence Heart software, Intellispace Cardiovascular 5.1 software, and EchoPAC version 112 software. The purpose of part 1 is to calculate the accuracy of the manually made measurements on the Ligence Heart software with other CE marked state-of-the-art software.

During part 2 of the study, investigators will analyze 2D TTE images and the results will be compared to the results of the analysis that automatic functionalities of Ligence Heart allow. The purpose of part 2 is to compare Ligence Heart automatic measurements precision and reliability with human physicians in real clinical setting.

Study Parts

UAB Ligence	Clinical Investigation Report	2021-04-09
		Rev: 1.0

Study Part	Functionalities tested	Comparator
Part 1	Manual	Other state-of-the-art CE marked medical images analysis software: Intellispace Cardiovascular 5.1 by PHILIPS, and EchoPAC version 112 software by GE
Part 2	Automatic	Cardiologists with expertise in echocardiology

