## 8 Study Data Collection and Assessments

### 8.1 Primary Assessment

For the primary objectives of the study the following measurement data will be collected:

Measurements performed on Ligence Heart and comparator software manually (Part 1):

- AoS (PLA)
- RVB (A4CH)
- LVEDV (A4CH)
- LVEDV (A2CH)
- RVEDA (A4CH)
- RAA (A4CH)
- AV-Vmax
- TR-Vmax
- E
- S'RV
- DEC
- ACT
- AV-VTI
- TR-VTI
- LVEDV (A2CH + A4CH)

Measurements performed by automatic functionalities of Ligence Heart and the comparator – the same measurements performed by cardiologists (Part 2):

- RAMAD (A4CH)
- AoA
- AoS
- STJ
- AAo
- LAD (PLA)
- LAV
- IVSd
- LVPWd
- LVEDD
- LVESD
- LVEDV (A4CH)
- LVESV (A4CH)
- LVEDV (A2CH)
- LVESV (A2CH)

UAB Ligence	Clinical Investigation Report	2021-04-09
		Rev: 1.0

- RAA
- RVB
- RVM
- RVOTPD
- RVEDARVESA

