## 12 Statistical Methods

### 12.1 Statistical Hypotheses

UAB Ligence	Clinical Investigation Report	2021-04-09
		Rev: 1.0

The following hypotheses will be tested with the statistical methods:

1. The manual functionalities of Ligence Heart provide equally accurate tools for echocardiography evaluation compared to other state of the art CE marked medical software.
2. Automatic functionalities of Ligence Heart software perform echocardiography image analysis with non-inferior accuracy compared to a cardiologist.
3. Automatic functionalities of Ligence Heart software perform echocardiography image analysis with lower intra-rater variability compared to a cardiologist.
4. Automatic functionalities produce measurement values faster than a cardiologist.

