## 16 Discussion and conclusions

### 16.1 Manual functionalities (Part 1)

Different types of manual measurements including area, distance and point measurements in B-mode and different spectral Doppler imaging modes have been tested and compared to two other CE marked medical image analysis platforms (EchoPAC by GE and Intellispace Cardiovascular by Philips). The measurement values obtained using the manual Ligence Heart functionalities did not show statistically significant variation when compared with other medical image analysis software. This proves that Ligence Heart can be used as medical image analysis software to analyze echocardiographic imaging data.

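### Hypothesis 1 claims equal accuracy, but it is tested by a difference test whose non-significance is read as proof; the named reliability endpoint has no acceptance value and no rule across 15 measurements

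*Protocol*

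**What the plan says.** Hypothesis 1 in section 12.1 of the Protocol reads: "The manual functionalities of Ligence Heart provide equally accurate tools for echocardiography evaluation compared to other state of the art CE marked medical software". No margin or criterion is attached, although section 6.1 says the analysis will lead to the hypotheses being accepted or rejected.

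The Part 1 primary endpoint in section 5.3.1 (and in the synopsis) is reliability: "The inter-software reliability between manual measurements performed with Ligence Heart and other CE marked state-of-the-art medical image viewers will be calculated". It is to be calculated; no value is said to be good enough.

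Section 12.4.2 plans three statistics. The first is a difference test: "Two-way ANOVA will be employed to test for significant differences between measurements made in different medical imaging software". The other two are descriptive: "Interrater reliability coefficient and Pearson correlation coefficient will be calculated to check the level of interchangeability between software". A table of verbal bands follows, with an edge between 0.80 and 0.81, but no band is made a condition for hypothesis 1. Section 8.1 lists 15 Part 1 measurements, and nothing says how many of them must pass.

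The same document reports the results. Section 15.1 (Manual functionalities) says "All tested measurements had inter-software reliability above 0.8, corresponding to high level of agreement between different platforms" and adds that no significant difference was found. Table 2 gives a point reliability for each measurement, without confidence limits, ANOVA p-values or Pearson coefficients. Section 16.1 rests its conclusion on the ANOVA: the values "did not show statistically significant variation when compared with other medical image analysis software", which it then treats as proof.

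**The concern.** The hypothesis is a claim of equality and the stated test is a test for difference. Non-significance can mean that the packages agree, or that the data are too noisy to separate them. The second reading grows more likely as measurement quality falls, so the criterion used in 16.1 rewards poor precision.

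Reliability behaves the other way: noise lowers it. A small systematic offset with precise measurements gives a significant ANOVA and high reliability. Large noise gives a non-significant ANOVA and low reliability. With no acceptance value for reliability and no rule across the 15 measurements, the plan does not say what hypothesis 1 requires when the two disagree. What is at stake is the support for the claim that the manual functions match two CE-marked packages.

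**Working it through.** **The plan's own figure.** The sample size of 54 in section 12.2 reproduces. With f = 0.25, 3 groups, 2 measurements and correlation 0.6, λ = f²·N·m/(1 − ρ) = 0.0625 × 54 × 2 / 0.4 = 16.875 on 2 and 51 degrees of freedom, and power is 0.956. Power is 0.948 at 52 and 0.952 at 53; rounding up to three equal groups gives 54. This is power to detect a difference (a group-by-time interaction). It says nothing about showing equality.

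**Inputs for the check.**
- t = 3 packages (section 7.1: "investigators will analyze the same images using Ligence Heart software, Intellispace Cardiovascular 5.1 software, and EchoPAC version 112 software"); m = 2 runs by one cardiologist (section 7.2).
- n = 58 (section 15.1, Demographic data), assumed to apply to Part 1.
- α = 0.05, given only in the sample size table and assumed for each ANOVA.
- Section 12.4.1 lists mean squares but no F ratio; F = MSR/MSSR is assumed.
- The variance components are assumptions, because the documents print none: patient variance 1, with interaction and error variances varied below.

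**Power of the ANOVA.** If one of three packages is shifted by d, the deviations from the mean are 2d/3, −d/3 and −d/3, and their squares sum to 2d²/3. So

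λ = m·n·(2d²/3) / (m·σ²_SR + σ²_e), on 2 and 114 degrees of freedom.

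For d = 0.10 the numerator is 2 × 58 × 0.00667 = 0.773.
- Low noise (σ²_SR = 0.02, σ²_e = 0.04): λ = 0.773/0.08 = 9.67, power 79%.
- High noise (σ²_SR = 0, σ²_e = 1): λ = 0.773/1 = 0.77, power 11%.

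**Reliability for the same settings.** The 12.4.1 coefficient is σ²_S/(σ²_S + σ²_R + σ²_SR + σ²_e), and the offset contributes d²/3 = 0.0033 to σ²_R.
- Low noise: 1/(1 + 0.0033 + 0.02 + 0.04) = 0.940. Without the offset it is 1/1.06 = 0.943, so the offset hardly moves it.
- High noise: 1/(1 + 0.0033 + 1) = 0.499.

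**Range over the assumed variances**, d = 0.10 (power from the formula; reliability as the simulated mean using the 12.4.1 estimators):

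| σ²_SR | σ²_e | ANOVA significant | mean reliability |
|---|---|---|---|
| 0.01 | 0.02 | 98% | 0.97 |
| 0.02 | 0.04 | 79% | 0.94 |
| 0.05 | 0.10 | 39% | 0.87 |
| 0.10 | 0.20 | 21% | 0.77 |
| 0 | 1 | 11% | 0.49 |

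The same offset is less likely to be flagged as reliability worsens. With high noise and no offset (n = 54), the ANOVA was non-significant and reliability was below 0.61 in 92% of simulated trials.

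**Would a reliability criterion be attainable?** The lowest value in Table 2 is RAA at 89.30%. A standard absolute-agreement confidence interval (n = 58, 3 packages, one value per cell as an approximation) gives a lower 95% limit of 0.84 if software variance is near zero, 0.815 if it is 20% of the non-patient variance, and 0.78 if it is 30%. Table 2 does not allow these cases to be told apart.

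**The case against.** **A lead statistic is named.** A reader might infer that Part 1 has no lead statistic at all. That goes too far: the synopsis and section 5.3.1 put inter-software reliability forward, and the 12.4.1 coefficient contains the software variance, so it penalises systematic offsets. What is missing is an acceptance value and a rule across 15 measurements.

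**Multiplicity.** A reader might also infer that 15 unadjusted ANOVA tests inflate the chance of a false success. They do not. With identical packages the chance of at least one p < 0.05 is 1 − 0.95^15 = 54% if the tests are independent and about 20% at an error correlation of 0.8. A figure such as one third needs a correlation of roughly 0.55 to 0.6. The documents give no such correlation; the 0.6 in section 12.2 is between repeats. More importantly, a chance rejection counts against the device. A Holm adjustment would make non-significance easier to reach: at its first step, 0.05/15, detection in the low-noise example falls from about 79% to about 43%.

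**Picking the winner.** A reader might suspect that the deciding statistic was chosen after seeing the data. Section 15.1 reports both criteria as met for every measurement, so no such choice is visible.

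**Scope.** Detail may sit in a statistical analysis plan that is not shown. That does not dispose of the point: section 12.4.2 states the test, section 16.1 draws the conclusion from it, and section 12.5.2 does name a primary and a secondary comparison for Part 2.

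It also stands that the variances are assumed, so 80% and 11% illustrate the behaviour of the test and are not properties of this trial.

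**Conclusion.** The point holds in this form: hypothesis 1 is a claim of equality, the stated test looks for differences, and 16.1 treats its non-significance as proof. Under the assumed variances, a 0.10 SD offset is detected in about 80% of trials at reliability 0.94 and in about 11% at reliability 0.50, so the two statistics can give opposite answers. That a non-significant difference test cannot show equality needs no assumption about variances.

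The high point reliabilities in Table 2 (89.30% to 99.26%) suggest that the data were not noisy, and nothing here shows that the manual functions perform badly. The fault lies in the inference and in the missing acceptance rule. It should be corrected, and the existing data suffice.

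**What to change.** - **Section 12.4.2:** make inter-software reliability, the endpoint already named in 5.3.1, the deciding statistic. Accept hypothesis 1 only if the lower 95% confidence limit exceeds 0.80 for each of the 15 measurements. Because all must pass, alpha need not be split.
- **Threshold:** 0.80 is the band edge in 12.4.2 and the line used in 15.1. The results are already known, so label it post hoc.
- **Table 2:** add the confidence limits.
- **ANOVA and Pearson:** treat as supportive only, without a Holm adjustment.
- **Section 16.1:** rest the conclusion on the reliability limits instead of on non-significance.

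The cost is wording in 12.4.2, 15.1 and 16.1 and a recalculation from data in hand. The downside is real: depending on the software variance component, the lower limit for RAA may come close to 0.80 or fall below it, and hypothesis 1 would then not be accepted under this rule.
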